## **2. LIST OF ABBREVIATIONS**

ADR	Adverse drug reaction
AE	Adverse Event
BI	Boehringer Ingelheim
CHD	Coronary heart disease
CKD	Chronic kidney disease
CVD	Cardiovascular disease
DMRP	Data management and review plan
eGFR	Estimated glomerular filtration rate
EMR	Electronic medical records
ENCEPP	European Network of Centers for Pharmacoepidemiology and Pharmacovigilance
ESRD	End stage renal disease
GPP	Good Pharmacoepidemiology Practice
HDL	High-density lipoprotein
ICD	International classification of disease
IDF	International Diabetes Federation
IEC	Independent Ethics Committee
IRB	Institutional Review Board
LDL	Low-density lipoprotein
LOS	Length of stay
MALB	Microalbumin
MI	Myocardial infarction
NIS	Non-interventional Study
PI	Principal Investigator
SEAP	Statistical and epidemiological analysis plan
SOP	Standard Operating Procedures
TC	Total cholesterol
TG	Triglyceride

### **4. ABSTRACT**

Name of company: Boehringer Ingelheim			
Name of finished medicinal product: NA			
Name of active ingredient: NA			
Protocol date: 18 March 2021	Study number: 1245-0203	Version/Revision: 3.0	Version/Revision date: 18 Jun 2021
Title of study:	Clinical characteristics and disease burden of patients with diabetes mellitus combined with cardiovascular or chronic kidney disease based on regional medical database in Tianjin China		
Rationale and background:	
Diabetes has been a major public health concern all over the world. According to the data from the International Diabetes Federation (IDF) Diabetes Atlas 2017, there are now around 425 million adults aged 20-79 worldwide living with diabetes. In China, the prevalence of diabetes among adults was 10.9%, representing an estimated 114.4 million Chinese adults with diabetes. The mortality among patient with diabetes was high, which estimated that 4 million adults died from diabetes worldwide in 2017. And diabetes has become a worrying burden upon the world's healthcare system recently. Studies have shown that the global health expenditure attributed to diabetes was estimated at USD 673 billion in 2015 and has risen to USD 727 billion 2017.
 
The heavy disease burden is mainly due to diabetic complications. Diabetes is a major risk factor for cardiovascular disease (CVD) and chronic kidney disease (CKD). The prevalence of CVD and CKD among patients with diabetes is high. Study suggested that diabetic kidney disease developed in up to 50 percent of diabetic patients at 20 years, with 15 percent having progressed to ESRD by this time. In the INTERHEART study, diabetes accounted for 10 percent of the population-attributable risk of a first myocardial infarction (MI). Compared to non-diabetes, the risk of CVD and CKD increased in patients with diabetes. A meta-analysis including 102 studies showed that patients with diabetes had an overall risk of coronary heart disease (CHD) twice that of patients without diabetes. Except for the risk of CVD and CKD, clinical characteristics and treatment patterns may also differ among patients with or without diabetes. Studies showed diabetic patients may have a greater burden of other risk factors than nondiabetics, such as hypertension, hyperlipidemia, and obesity. Compared with individuals without diabetes, those with diabetes have a greater extent of coronary ischemia and are more likely to have a MI and silent myocardial ischemia. Moreover, the effect of treatment on patients with or without diabetes may differ, thus the treatment patterns may be different.
 
China has been identified with the largest absolute disease burden of diabetes in the world recently. Diabetic patients with established CVD or CKD are bringing growing pressure upon our nation's healthcare expenditure.
		

	
However, the characteristic profile of Chinese diabetic patients who have CVD, CKD or are at high risk of CVD remains unclear thus is in urgent need for in-depth investigation. Several studies have shown that diabetes patients often suffer from multiple comorbidities, including the CVD and clearly described the characteristics and treatment patterns of such patients. However, patient characteristics and treatment patterns may differ across regions and hospitals. Lack of adequate understanding of such information may result in suboptimal management of patients and policy decisions. This is particularly true in China. In current China, however, the information regarding diabetes or non-diabetes patients who also had other comorbid conditions (e.g. established CV diseases, CKD or at high risk for such problem), is limited; the patient characteristics, treatment patterns and economic burden may not be fully understood. The treatment outcomes may be improved with better understanding about the current treatment pattern, patient characteristics, and potential treatment gap.
 
Regional medical data has received a lot of attention for its advantages on larger sample size and better representation of the general population. Tianjin regional database, which cover individual-level health information, is a valuable data source for clinical studies. Through integrating EMR systems of hospitals by patient unique identify code, the database contains comprehensive information regarding clinical care, such as patients' basic information, medical advice, diagnosis, laboratory examination, medical records and medical costs. Till now, data from 40 tertiary hospitals has been collected, and there were approximately 600,000 patients diagnosed with diabetes in these 40 tertiary hospitals from 01/01/2015 to 31/12/2019. Of these, 100,000 patients were with comprehensive information through integrating EMR systems.
 
Therefore, based on Tianjin regional database, we will describe the demographic, clinical characteristics, treatment, and economic burden of disease of Chinese diabetic/non-diabetic patients with/without established CVD, CKD, or at high CV risk including hypertension and hyperlipidemia. And we believe that the resulting findings will provide relevant evidence to achieve better healthcare for diabetes patients with established or at high risk of CVD or CKD.

Research question and objectives:	The study aims to investigate the clinical characteristics, treatment, and economic burden of disease of Chinese diabetic/non-diabetic patients with/without established cardiovascular disease, chronic kidney disease, or at high cardiovascular risk
Study design:	Non-interventional study based on regional medical database
Population:	We will include diabetic/non-diabetic patients with/without established cardiovascular disease, or chronic kidney disease, or at high cardiovascular risk in Tianjin regional database from 01/01/2015 to 31/12/2019. We will exclude patients with non-Chinese nationalities, or duplicated storage (records with same inpatient code).
Variables:	Diabetes or not, demographic characteristics, comorbidities, complications, treatment pattern and economic burden, outcome variables
Data sources:	Tianjin regional database from 01/01/2015 to 31/12/2019, it comprises of EMR system data from 40 tertiary hospitals.

Study size:	This study is a database research project using an established regional database in Tianjin. From 01/01/2015 to 31/12/2019, about 600,000 patients diagnosed as diabetes in Tianjin. Of which, 100,000 patients contained comprehensive information about patients' basic information, medical advice, diagnosis, laboratory examination, medical records and medical costs.
Data analysis:	
 
1) Description of the patient demographic characteristics, comorbidities, complications, treatment pattern and economic burden. Characteristics presented as continuous data will be summarized through means, standard deviations, medians, minimum and maximum values; whereas, categorical data will be summarized as counts and proportions.
 
2) All tests will be two-sided unless otherwise specified
 

Milestones:	
 
- EC approval 06/2021
 
- Start of data collection 07/2021
 
- End of data collection 08/2021
 
- Final results 10/2021
 
- Final NIS report 12/2021
 
 
Publication Plan – Submission Date
 
 
- Abstract: 11/2021
 
- Oral presentation: 12/2021
 
- Full paper: 03/2022
 

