## **8. RESEARCH QUESTION AND OBJECTIVES**

The study aims to investigate the clinical characteristics, treatment, and economic burden of disease of Chinese diabetic/non-diabetic patients with/without established cardiovascular disease, chronic kidney disease, or at high cardiovascular risk, including:

[figure not shown]
- Primary objectives: describe the proportion of Chinese diabetic/non-diabetic patients with established cardiovascular disease, CKD, or at high cardiovascular risk including hypertension and hyperlipidemia.
- Secondary objectives: describe the demographic characteristics of the last visit for all patients, and the demographic characteristics of inpatients over time; investigate the clinical characteristic for all patients.
- Further objectives: examine economic burden of disease of Chinese diabetic/non-diabetic patients with/without established cardiovascular disease, CKD, or at high cardiovascular risk; explore the trends of clinical characteristics, treatment patterns, economic burden of inpatients over time.

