**9.3.2.2 Secondary outcomes**

1. The demographic characteristics of the latest visit for all patients, as well as the trends for inpatients over time (2015, 2017, and 2019 respectively):
  - 1) Age at admission
  - 2) Gender
  - 3) Insurance payment
2. The clinical characteristics of the studied population of the latest visit for all patients, as well as the trends for inpatients over time (2015, 2017, and 2019 respectively):
  - 1) Discharge department
  - 2) Death
  - 3) Laboratory test results:
    - a) HbA1c
    - b) random blood glucose
    - c) serum creatine

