6.2 SETTING

After considering the availability, feasibility, coverage, number of included population and data integrity, this study is based on Tianjin regional medical database from 01/01/2015 to 31/12/2019.

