7.2.2 Secondary outcomes

- 1) The demographic characteristics of the latest visit for all patients, as well as the trends for inpatients over time (2015, 2017, and 2019 respectively). Clinical characteristics of outpatients and hospitalized patients will be described respectively.

Table 2. The demographic and clinical characteristics of the latest visit

| Outpatients | | | | Inpatients | | | | Total patients |
|--|----------------|----------------|----------------|-------------------|----------------|----------------|----------------|-----------------------|
| Group A | Group B | Group C | Group D | Group A | Group B | Group C | Group D | |
| Demographic characteristics in 2015 | | | | | | | | |
| Age (mean, sd) | | | | | | | | |
| Gender (n, %) | | | | | | | | |
| Insurance payment (n, %) | | | | | | | | |
| Demographic characteristics in 2017 | | | | | | | | |
| Age (mean, sd) | | | | | | | | |
| Gender (n, %) | | | | | | | | |
| Insurance payment (n, %) | | | | | | | | |
| Demographic characteristics in 2019 | | | | | | | | |
| Age (mean, sd) | | | | | | | | |
| Gender (n, %) | | | | | | | | |
| Insurance payment (n, %) | | | | | | | | |

Note Group A Diabetes with cardiovascular disease, chronic kidney disease or at high cardiovascular risk; Group B Diabetes without cardiovascular disease, chronic kidney disease or at high cardiovascular risk; Group C Non-diabetes with cardiovascular disease, chronic kidney disease or at high cardiovascular risk; Group D Non-diabetes without cardiovascular disease, chronic kidney disease or at high cardiovascular risk;

2) The clinical characteristics of the studied population of the latest visit for all patients, as well as the trends for inpatients over time (2015, 2017, and 2019 respectively). Clinical characteristics of outpatients and hospitalized patients will be described respectively.

Table 3. The clinical characteristics of the latest visit

| Outpatients | | | | Inpatients | | | | Total patients |
|---|----------------|----------------|----------------|-------------------|----------------|----------------|----------------|-----------------------|
| Group A | Group B | Group C | Group D | Group A | Group B | Group C | Group D | |
| Clinical characteristics in 2015 | | | | | | | | |
| Department of discharge | | | | | | | | |
| Death | | | | | | | | |
| Clinical characteristics in 2017 | | | | | | | | |
| Department of discharge | | | | | | | | |
| Death | | | | | | | | |

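### The secondary-outcome inpatient trends are tabulated for 2015, 2017 and 2019 only, although the data cover all five years; adding 2016 and 2018 is a cheap, optional improvement

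*Protocol*

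**What the plan says.** Both documents set the same five-year window. The Protocol abstract describes the source as "Tianjin regional database from 01/01/2015 to 31/12/2019, it comprises of EMR system data from 40 tertiary hospitals", and SAP 6.2 agrees: "this study is based on Tianjin regional medical database from 01/01/2015 to 31/12/2019".

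Change over time is a stated aim. In Protocol 8 the secondary objectives include inpatient demographics over time, and the further objectives are to "explore the trends of clinical characteristics, treatment patterns, economic burden of inpatients over time".

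Protocol 9.3.2.2 then narrows the years. Its first secondary outcome is "The demographic characteristics of the latest visit for all patients, as well as the trends for inpatients over time (2015, 2017, and 2019 respectively"; its second, which includes discharge department, death, HbA1c, random blood glucose and the serum creatinine measure, carries the same three years. SAP 7.2.2 repeats the restriction. The shells of SAP Tables 2, 3 and 4 have one block for each of 2015, 2017 and 2019 (for example "Demographic characteristics in 2017") and none for 2016 or 2018.

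SAP Table 1, for the primary proportions, is laid out differently. Its columns run 2015, 2016, an ellipsis, 2019 and Overall, each split into outpatients and inpatients.

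**The concern.** Two of the five available years are missing from the tables meant to show how inpatient characteristics changed. Yearly inpatient figures are planned for Table 1, so availability does not explain the gap, and the visible text offers no other reason.

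The plan is descriptive. SAP 10.1 names t tests, analysis of variance, chi-square and rank tests, but no trend test and no model for time. Readers will therefore judge the trends by eye, by whether the values go steadily up or down. The number of years matters for that judgement. More patients per year reduce sampling error within a year. They do not reduce real variation between years, for example in coding or case mix. Protocol 9.9 itself notes that hospitals may understand the ICD codes differently.

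At stake is the reliability of statements that an inpatient characteristic rose or fell over the period, and the ability to see what happened in 2016 and 2018. The primary outcome is not at stake.

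**Working it through.** The documents give no precision, power or between-year standard deviation for these trends, so there is no planned figure to reproduce. The check compares three yearly values with five.

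**Inputs**
- Years available: 2015, 2016, 2017, 2018, 2019, so k = 5 (Protocol 4; SAP 6.2).
- Years tabulated for the secondary inpatient trends: 2015, 2017, 2019, so k = 3 (Protocol 9.3.2.2; SAP 7.2.2, Tables 2 to 4).
- Assumption, not from the documents: there is no true trend and the yearly values are exchangeable, so every ordering is equally likely and ties are ignored.

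**Chance of a steady rise or fall with no trend**

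Of the k! possible orderings, one rises throughout and one falls throughout, so the chance is 2/k!.
- Three years: 2/3! = 2/6 = 33%.
- Five years: 2/5! = 2/120 = 1.7%.

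**Scale across the tables**

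Tables 2 to 4 list eight characteristics: age, gender, insurance payment, discharge department, death, HbA1c, random blood glucose and serum creatinine. Taking one series per characteristic in each of the four inpatient groups gives 8 × 4 = 32 series. Under the same assumption the expected number that look steadily rising or falling by chance is 32 × 2/6 = 10.7 with three years, and 32 × 2/120 = 0.5 with five.

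**Sensitivity to the assumption**

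If fluctuations instead accumulate from year to year (a walk with independent symmetric steps and no drift), three values involve two steps and five values four.
- Three years: 2 × (1/2)² = 50%.
- Five years: 2 × (1/2)⁴ = 12.5%.

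The direction is the same, but the contrast is smaller.

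**What the three years do keep**

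For a straight line through yearly values, Sxx is the sum of squared distances of the years from 2017.
- Three years: 4 + 0 + 4 = 8.
- Five years: 4 + 1 + 0 + 1 + 4 = 10.

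For a given year-to-year standard deviation, the slope's standard error with three years is √(10/8) = 1.118 times that with five, or 12% larger. The estimated slope therefore loses little. The loss lies in judging it against fluctuation, because residual degrees of freedom are 3 − 2 = 1 instead of 5 − 2 = 3.

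**What the three years do not show**

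A departure confined to 2016 or 2018 does not appear in these tables. A lasting change that starts in 2016 is first seen in 2017 and looks the same as one that starts in 2017.

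**The case against.** The best defence is that these are prespecified snapshot years for descriptive secondary tables. They are evenly spaced, keep both endpoints and are stated consistently in both documents. The Protocol calls the study cross-sectional, its ENCePP checklist marks hypotheses and measures of association as not applicable, and dating a change to a particular year is not an objective. Three years also retain 8/10 = 80% of Sxx. All of this stands, and it keeps the point minor. It gives no reason to leave out years that are already in the data window.

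Four stronger readings are tempting, and the documents do not support them.
- A reader might infer that all inpatient trends rest on three years, or that 2016 and 2018 are discarded. Table 1 gives inpatient columns by year, and nothing removes those years from the group definitions or the latest-visit description.
- A reader might fit a line to the yearly values and report a 95% interval about 4.5 times wider with three years (12.706/√8 = 4.49 against 3.182/√10 = 1.006 year-to-year standard deviations per year). The arithmetic is right, but the visible plan contains no such regression, so the figure does not measure a loss in any planned analysis.
- A reader might infer that Tables 2 to 4 cannot be compared with Table 1. They can for the shared years: 2015 and 2019 are named columns, and 2017 falls within the ellipsis.
- A reader might extend the restriction to treatment patterns and economic burden. The years for those trends are not in the visible text, and the section numbering suggests that text has been withheld. A reason for the three years could also be there, so the absence of a reason holds only for what can be read.

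**Conclusion.** The point holds in a limited form. The restriction to 2015, 2017 and 2019 is explicit for the secondary-outcome inpatient trends, the other two years lie within the data window, and no reason is visible. Three values make a weak description of a trend: a steady rise or fall arises by chance 33% of the time, against 1.7% for five. Those figures rest on exchangeable yearly fluctuation and on reading a steady run as a trend. With accumulating fluctuation they become 50% and 12.5%.

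It would go too far to say that three years cannot separate a trend from fluctuation. They do so poorly, and five years is still a short series. The primary proportions are unaffected. Severity is low, and the change is optional.

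**What to change.** In Protocol 9.3.2.2 (both secondary outcomes) and SAP 7.2.2 (both items), replace the list of three years with each year from 2015 to 2019. Add 2016 and 2018 inpatient blocks to SAP Tables 2, 3 and 4, following the yearly layout of Table 1.

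If the three years are kept, give the reason and call the result a comparison of three selected years rather than a trend.

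The cost is two more blocks in each of three tables, from data already in the extraction window. The tables become longer. No new data source, group definition or statistical method is needed.

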## 5. AMENDMENTS AND UPDATES

Version Number	Revision Date	Rationale for Amendment
1.0	18 Mar 2021	NA
2.0	08 May 2021	
 
1. Updated the organization of PI
 
2. Updated the milestones based on the current progress
 
3. Supplemented some information under the study sites
 
4. Separated Heart Failure from other CVDs under inclusion criteria according to the further outcome
 
5. Clarified the method how to protect patient privacy
 
6. Specified the time period of data source
 

3.0	18 Jun 2021	
 
1. Amended the study title according to the objectives
 
2. Specified the criteria for grouping and indicator details
 
3. Updated the milestones based on the current progress
 
4. Updated the version & date of DMRP and SEAP
 

Amendment 1:

CHANGE 1: Updated the organization of PI
Section of the Clinical Trial Protocol: 3
Principal Investigator (PI)

Was changed to:
Principal Investigator (PI)
Reason(s) for change 1:
PI participates in this study as a member of [REDACTED] instead of [REDACTED]
CHANGE 2: Updated the milestones based on the current progress
Section of the Clinical Trial Protocol: 4 & 6

 
- EC approval 03/2021
 
- Start of data collection 04/2021
 
- End of data collection 05/2021
 
- Final results 10/2021
 
- Final NIS report 12/2021
 

Was changed to:

 
- EC approval 05/2021
 
- Start of data collection 06/2021
 
- End of data collection 07/2021
 
- Final results 10/2021
 
- Final NIS report 12/2021
 

Reason(s) for change 2:
Updated based on the current progress
CHANGE 3: Supplemented some information under the study sites
Section of the Clinical Trial Protocol: 9.2.1
This study is based on Tianjin regional database (managed by [REDACTED]), which covers individual-level health information from 15 million residents in Tianjin. Till 2020, data from 40 tertiary hospitals has been collected, and we will use data from these 40 tertiary hospitals.
Was changed to:
This study is based on Tianjin regional database which is approved by Tianjin Municipal Health Commission and managed by [REDACTED], and authorized to [REDACTED] for this study use. It covers individual-level health information from 15 million residents in Tianjin. Till 2020, data from 40 tertiary hospitals has been collected, and we will use data from these 40 tertiary hospitals. The study was co-sponsored by [REDACTED] of the Health Data Special Committee of the [REDACTED], who was responsible for the research protocol design, as well as data cleaning, data analysis and final research report writing, and [REDACTED] of [REDACTED] as Co-PI who will be responsible for the research design.

Reason(s) for change 3:
Clarified the relationships between the organizations and the 2 Co-PIs.
CHANGE 4: Separated Heart Failure from other CVDs under inclusion criteria according to the further outcome
Section of the Clinical Trial Protocol: 9.2.2

Inclusion Criteria:
 
 
1) Patients in the Tianjin regional database from 2015 to 2019.
 
2) Group A: patients with diagnosis of diabetes, and with diagnosis of cardiovascular disease, or chronic kidney disease or at high cardiovascular risk;
 
3) Group B: patients with diagnosis of diabetes, but not with diagnosis of cardiovascular disease, chronic kidney disease or at high cardiovascular risk;
 
4) Group C: patients with diagnosis of cardiovascular disease, or chronic kidney disease or at high cardiovascular risk, but not with diagnosis of diabetes;
 
5) Group D: patients without diagnosis of cardiovascular disease, chronic kidney disease or at high cardiovascular risk, and without diagnosis of diabetes. We will randomly select a group of non-diabetic patients without any of the above diseases by matching on age and gender.
 
 
Definition of diabetes, cardiovascular disease, chronic kidney disease and high cardiovascular risk:
 
 
• Diabetes: patients with at least 1 discharged diagnosis or 2 outpatient diagnosis of diabetes (the first diagnosis will be the index diagnosis, and the time interval between diagnoses is not restricted) (International classification of disease (ICD)-10 E10-E14)
 
• Cardiovascular disease: patients with at least 1 discharged diagnosis or 2 outpatient diagnosis of ischemic heart diseases (the first diagnosis will be the index diagnosis, and the time interval between diagnoses is not restricted) (ICD-10 I20~I25); or patients with at least 1 discharged diagnosis or 2 outpatient diagnosis of cerebrovascular diseases (the first diagnosis will be the index diagnosis, and the time interval between diagnoses is not restricted) (ICD-10 I60~I69); or patients with at least 1 discharged diagnosis or 2 outpatient diagnosis of ischemic peripheral artery disease (the first diagnosis will be the index diagnosis, and the time interval between diagnoses is not restricted) (ICD-10 E10.501, E11.603, E14.501, E14.606, E14.503, I73.9, I99.03, I99.04); or patients with at least 1 discharged diagnosis or 2 outpatient diagnosis of heart failure (the first diagnosis will be the index diagnosis, and the time interval between diagnoses is not restricted) (ICD-10 I50);
 
• Chronic kidney disease: inpatients with at least once 1 discharged diagnosis CKD (ICD-10 N18), or inpatients with the last estimated glomerular filtration rate (eGFR, calculated by CKD-EPI equation) <60 mL/min/1.73 m^2 or prescription of dialysis, but not with the diagnosis of acute kidney injury (ICD-10 N17); or outpatients with at least 2 diagnosis of CKD (the first diagnosis will be the index diagnosis, and the time interval between diagnoses is not restricted) or with two consecutive eGFR (calculated by CKD-EPI equation) <60 mL/min/1.73 m^2 by 90 days or more.
 
• High cardiovascular risk: patients with at least 1 discharged diagnosis or 2 outpatient diagnosis of hypertension (the first diagnosis will be the index diagnosis, and the time interval between diagnoses is not restricted) (ICD-10 I10~I15); or at least 1 discharged diagnosis or 2 outpatient diagnosis of hyperlipidemia (ICD-10 E78.001-E78.003, E78.101, E78.203, E78.301-E78.304, E78.306, E78.401, E78.501, E78.902)
 

Was changed to:

